9.14. Foreseeable Complications

There are no foreseeable complications with recruitment or completion of the study in general. All units have already been prepared for trial. Complications relating to adherence to the study protocol and NHF therapy use are outcome measures of this study.

10. CLINICAL TRIAL DOCUMENTATION

10.1. Consent and Recruitment

NZ specific and USA specific information sheets and consent forms are to be used, as approved by their local regulatory body.

10.2. Case Report Forms

The CRFs are to be filled in by hand, see Data Collection SOP. CRFs are to be scanned to Fisher and Paykel who will then enter data into an electronic database.

10.3. Insurance Statement

A copy of the insurance statement is shown in Appendix 3. This is to document that compensation to subjects(s) for trial related injury will be available.

10.4. Record of Deviations

This version of the protocol has been completed prior to participant recruitment, there are no deviations to date.

11. STATISTICAL CONSIDERATIONS

11.1. Description of the Statistical Design

As this is a feasibility study the primary outcome variable (9.4.1) will be expressed as the mean number of hours per day used, with standard deviation. The mean may be weighted for time in the study and allocated 95% confidence intervals for each by weighted regression.

Continuous outcomes 9.4.2-4, 9.4.11, 9.4.13, 9.4.18c, and 9.4.26 will also be expressed as mean, standard deviation. Means may be weighted for time in the study and allocated 95% confidence intervals for each by weighted regression.

For the mean number of hospital readmissions (9.4.18a), ED visits (9.4.21a) and GP visits (9.4.24) Poisson regression will be used.

Time to first hospital readmission (9.4.18b) and first ED visit (9.4.21b) will be analyzed by Kaplan-Meier survival estimates and CI for quantiles of survival, those who don't get admitted within the study time will be censored data.

Categorical outcomes 9.4.5-10, 9.4.12, 9.4.14, 9.4.16, 9.4.17, 9.4.19, 9.4.20, 9.4.22, 9.4.23 and 9.4.25 will be described by absolute numbers and proportions. Confidence intervals may be calculated for outcomes 9.4.5-10, 9.4.12, 9.4.14, 9.4.16, 9.4.19, and 9.4.22.

NHF questionnaire results (9.4.15) will likely be presented by mean, standard deviation and confidence interval, however if the data distribution is heavily skewed data may be presented as proportions.

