9.4. End Points

The following end points will be evaluated:

Primary outcome:

The primary outcome will be NHF use for 30 days following discharge after AECOPD. Use will be expressed as hours of myAIRVO 2 use per day over 30 days, as obtained by myAIRVO 2 electronic monitoring.

Secondary outcomes:

Other use variables:

- i. Number of days of use, adjusted for number of days with myAIRVO 2 at home
- ii. Average use per day of myAIRVO 2 during week 1, week 2, week 3 and week 4.
- iii. Average use per day on days of myAIRVO 2 use

Withdrawals and exclusions:

- i. Proportion of participants screened that were excluded
- ii. Reason for exclusion
- iii. Proportion of participants enrolled that were withdrawn
- iv. Reason for withdrawal

Participants requiring oxygen delivery via myAIRVO 2:

- i. Proportion of participants using domiciliary oxygen

Aspects of myAIRVO 2 use:

- i. Proportion of participants who reported having reduced myAIRVO 2 flow settings from the initial flow
- ii. Reduction in flow
- iii. Proportion of participants who reported having increased myAIRVO 2 flow settings from the initial flow
- iv. Increase in flow
- v. Proportion of participants who reported having reduced myAIRVO 2 temperature setting from the initial setting
- vi. NHF therapy Questionnaire results

Clinical outcomes

- i. Proportion of participants with at least one hospital readmission within 30 days of discharge
- ii. Reasons for hospital admissions (AECOPD, other respiratory cause or other cause)
- iii. In those that had at least one hospital readmission:
 - a. Number of readmissions
 - b. Time to first hospital readmission
 - c. Hospital readmission length
- iv. Proportion of participants with at least one ED visit within 30 days of discharge
- v. Reason for ED visits (AECOPD, other respiratory cause or other cause)
- vi. In those that had at least one ED visit:
- vii. Number of ED visits
- viii. Time to first ED visit
- ix. Proportion of participants with at least one GP visit within 30 days of discharge
- x. Reason for GP visits (AECOPD, other respiratory cause or other cause)
- xi. In those that had at least 1 GP visit within 30 days of discharge: number of GP visits
- xii. LACE Index for hospital admissions
- xiii. Lung function measurements (FEV₁, SVC_{in} and FVC) at day 1 and 31.

* An ED visit is counted if the patient went to ED for assessment and was not subsequently admitted to a hospital ward.

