11.6. Selection Criteria

For endpoint details see section 9.4. All participants who were screened to take part in the study will be included in the analysis of endpoint 2.b.i. All patients who were discharged with a myAIRVO 2 device to take home will be included in analysis of all other endpoints.

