12.2. Foreseeable Adverse Events

Participants may wish to discontinue NHF therapy should they find it uncomfortable. Adverse events are expected, including death, hospital and Intensive Care Unit admissions and patient deterioration as part of disease progression.

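### Section 9.4 restricts visit counts and times to first event to participants who had the event; this contradicts the censoring in 11.1 and, if followed, makes the ordinary Poisson intervals wrong

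*Combined protocol and SAP*

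**What the plan says.** Section 11.1 refers to the endpoints by a running count through the list in 9.4. Counting that list in order gives 16 for the proportion readmitted, 18a to 18c for the readmission details, 19 for the proportion with an ED visit, 21a and 21b for the ED details, 22 for the proportion with a GP visit and 24 for the GP count. These match the labels in 11.1.

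- **Section 9.4, readmission.** Number, time to first and length (18a, 18b, 18c) stand under the lead-in "In those that had at least one hospital readmission".
- **Section 9.4, ED.** Number and time to first (21a, 21b) follow the lead-in "In those that had at least one ED visit". They are printed as separate list items, but the labels 21a and 21b in 11.1 confirm that they belong under it. A footnote adds: "An ED visit is counted if the patient went to ED for assessment and was not subsequently admitted to a hospital ward".
- **Section 9.4, GP.** Item 24 reads "In those that had at least 1 GP visit within 30 days of discharge: number of GP visits".
- **Section 11.1, times.** Items 18b and 21b are analysed by Kaplan-Meier with confidence intervals for quantiles, and "those who don't get admitted within the study time will be censored data".
- **Section 11.1, counts.** "For the mean number of hospital readmissions (9.4.18a), ED visits (9.4.21a) and GP visits (9.4.24) Poisson regression will be used". No denominator, offset or zero truncation is stated.
- **Section 11.6.** Apart from one screening endpoint, "All patients who were discharged with a myAIRVO 2 device to take home will be included in analysis of all other endpoints".

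No section reconciles the lead-ins in 9.4 with 11.1 and 11.6.

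**The concern.** For the times, the sections define two different sets of people. Censoring participants for not having the event requires that they are in the analysis, and the lead-ins in 9.4 take them out.

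For the counts, the conflict is between 9.4 and the general rule in 11.6, because 11.1 cites the event-only items without giving a denominator. If 9.4 is followed, every count is at least 1. Ordinary Poisson regression assumes a variance equal to the mean and gives zero a positive probability, so its interval does not describe such data.

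Objective 5 in section 8.2 asks for readmission, ED and GP visit rates to plan the randomized trial. Two analysts, one following 9.4 and one following 11.6, would report different quantities under the same name.

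**Working it through.** **Inputs.** N = 80, the minimum in 11.2; the planned 100 reproduces as 80/(1 − 0.20) = 100 and is not in question. The 30-day readmission rate is 21%, the USA figure in 7.2 and the only all-cause rate in the documents. Expected participants readmitted: 0.21 × 80 = 16.8, taken as 17. The documents do not say how many are readmitted more than once. I assume 15 with one and 2 with two, so 19 readmissions, and vary this below. Follow-up is taken as complete.

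**1. Times, by logic.** In the event-only set all 17 have an event, nobody is censored for lacking one, and the curve falls to 0 by day 30. In the full cohort 63 of 80 are censored and the curve ends at 63/80, about 0.79. One data set cannot give both.

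The event-only time also says little about the event rate. With a constant hazard, its median solves F(t) = p/2 with hazard −ln(1 − p)/30. At p = 0.21 this is −ln(0.895)/(0.2357/30) = day 14.1. At a third of that rate, p = 0.07, it is day 14.7.

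**2. Counts, event-only (9.4 followed).** For an intercept-only Poisson model, SE(mean) = √(total)/n and the 95% CI is mean × exp(±1.96/√total).

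- Mean = 19/17 = 1.118.
- Poisson SE = √19/17 = 0.256.
- exp(1.96/√19) = 1.568, so the CI is 1.118/1.568 to 1.118 × 1.568 = 0.71 to 1.75. The lower limit is below 1, the smallest value possible.
- Empirical SE: the squared deviations sum to 15 × 0.118² + 2 × 0.882² = 1.765; √(1.765/16/17) = 0.081.
- Ratio 0.256/0.081, about 3.

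Other splits of the 17: with 4 having two readmissions, mean 1.24, CI 0.81 to 1.90; with 6, mean 1.35, CI 0.90 to 2.04. Both lower limits stay below 1.

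**3. The same without an assumed split.** For a zero-truncated Poisson with P(event) = p: lambda = −ln(1 − p), mean m = lambda/p, variance m(1 + lambda − m). The ordinary Poisson SE is too large by √(m/variance) = 1/√(1 + lambda − m). At p = 0.21, lambda = 0.2357 and m = 1.1225, so the factor is 1/√0.1132 = 2.97.

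The factor falls as events become commoner: 2.1, 1.6 and 1.3 at assumed proportions of 40%, 60% and 80%.

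**4. Counts, full cohort (11.6 followed).** Mean = 19/80 = 0.2375; Poisson SE = √19/80 = 0.0545; CI 0.2375/1.568 to 0.2375 × 1.568 = 0.15 to 0.37. The empirical SE with the 63 zeros kept is 0.0541, so ordinary Poisson regression is sound here.

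**5. Side checks for the full cohort.** With 80 participants and no early censoring, the median needs 40 events and the lower quartile 20, against 16.8 expected. The binomial probability of 20 or more at 21% is 0.23. The 10th percentile needs 8 events and is reached with probability 0.997.

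For deaths, assume constant cause-specific hazards, a true 21% readmitted, and 2%, 5% or 10% dying without readmission. Censoring the deaths then gives a Kaplan-Meier 30-day proportion of 21.2%, 21.6% or 22.2%.

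**The case against.** **The intended analysis of the times can be identified.** Section 11.1 is the statistical section and 11.6 agrees with it; two analysis sections stand against list lead-ins. This stands. A reader might infer that the times will be reported from an event-only set. The documents do not support that, because it would mean setting aside both 11.1 and 11.6. What remains is that 9.4 still says otherwise and nothing says which governs.

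**The count error is conditional.** It arises only if 9.4 is followed. Under 11.6 the zeros are kept and Poisson is adequate (step 4). Even on the 9.4 reading the conditional mean is estimated correctly, the interval errs on the wide side, and the point estimate converts exactly: 17/80 × 19/17 = 0.2375. All of this stands. It does not rescue an interval that extends to impossible values, nor settle which mean is meant.

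**Larger figures are tempting.** Section 7.2 also gives 7% and 8%, at which the SE factor would be 5.3 and 4.9. Those rates are for readmission with a primary diagnosis of AECOPD, whereas items 16 and 18 count readmission for any cause, so they do not apply. Nor can the readmission figure be carried over to ED or GP visits: the documents give no rates for these, and the factor shrinks as events become commoner.

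**Competing deaths and unreached quantiles might be read as further errors.** They are not part of the contradiction. Section 12.2 does foresee deaths ("Adverse events are expected, including death, hospital and Intensive Care Unit admissions"), but under the assumed death rates the effect is 0.2 to 1.2 percentage points.

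**Conclusion.** The concern holds in this form. For 18b and 21b, 9.4 and 11.1 cannot both be followed; 11.1 and 11.6 suggest that the full cohort was intended. For 18a, 21a and 24 the denominator is unsettled, and on the 9.4 reading the ordinary Poisson interval is wrong: for readmission at 21% its SE is about 3 times too large and its lower limit is below 1.

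That size rests on the 21% background rate, N = 80, complete follow-up and the assumed split; the factor of 2.97 in step 3 replaces the split with a Poisson assumption. Nothing can be quantified from the documents for ED or GP visits.

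The impact is minor to moderate. A reader might infer that planning of the randomized trial is compromised. It is not: the 30-day proportions with at least one event (items 16, 19, 22) are unaffected and 11.1 allows confidence intervals for them. The primary outcome and the sample size are also untouched.

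**What to change.** - **Section 9.4:** move 18a, 18b, 21a, 21b and 24 out from under the event-only lead-ins.
- **Sections 9.4 and 11.1:** state that these five items are analysed in all participants discharged with a device.
- **Counts:** keep the zeros, use log follow-up time as an offset, and report events per participant per 30 days with a 95% CI.
- **Times:** censor participants without the event in question at withdrawal or day 30, and word this separately for readmission and ED visit. The present clause speaks only of admission, while the footnote in 9.4 counts an ED visit only when no admission follows. A participant who was admitted but had no countable ED visit therefore has no stated rule.
- **Event-only summaries,** including readmission length (18c): keep as descriptive.

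Optional refinements: treat death without the event as a competing event, and report the 30-day Kaplan-Meier proportion with its CI beside any quantiles reached, since at 21% the median will not be reached and the quartile probably not.

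The cost is wording in two sections and little programming. No new data are needed; deaths are already reported as serious adverse events under 12.3.

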11.2. Sample Size

The NZ site and USA site will recruit 20 and 80 patients, respectively. These values are based on an estimated drop-out rate of 20% and the requirement for a minimum of 80 patients in total to assess feasibility and provide robust information in respect of appropriate outcome measures.

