12.3. Reporting Adverse Events

For the purposes of this study the following events will be considered to be serious adverse events (SAEs):

- Death
- Life-threatening event

- Permanently disabling or incapacitating event
- Hospitalisation or prolongation of hospitalisation. Hospitalisation for the purposes of SAE reporting is defined as an admission to hospital and does not include a presentation to the ED followed by discharge without admission or an admission for elective reasons
- Any event considered serious by the study investigator

SAEs will be reported to the Sponsor (Fisher and Paykel Healthcare) within 24 hours of the investigator becoming aware of the event on the study SAE form. Other adverse events will also be reported to the Sponsor within seven days.

Other adverse events (AEs) will be reported to the Sponsor (Fisher and Paykel Healthcare) within 7 days of the investigator becoming aware of the event on the study AE form.

Device deficiencies (related to the identity, quality, durability, reliability, safety or performance of a device) will be reported to the Sponsor (Fisher and Paykel Healthcare) in writing. If the investigator deems the event could have led to a serious adverse event, it must be reported within 24 hours of the investigator becoming aware of it, otherwise it should be reported within 7 days. The sponsor will manage device deficiency reports as part of its ongoing post marketing safety review process and the investigator will supply the sponsor with additional safety information as required.

Adverse events and device deficiencies will be reported to the HDEC, IRB, Medsafe and FDA as required

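### Section 11.1 has one admission-based censoring rule for two time-to-event outcomes; taken literally, it censors most first ED visits (9.4.21b), so each outcome needs its own rule

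*Combined protocol and SAP*

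**What the plan says.** Section 11.1 names both outcomes together: "Time to first hospital readmission (9.4.18b) and first ED visit (9.4.21b) will be analyzed by Kaplan-Meier survival estimates". The same sentence ends with the only censoring rule in the document, which applies to participants who do not "get admitted within the study time will be censored data". It gives no censoring time.

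The footnote to section 9.4 defines the ED event: "An ED visit is counted if the patient went to ED for assessment and was not subsequently admitted to a hospital ward". Section 12.3 keeps the same distinction for safety reporting, where hospitalisation "does not include a presentation to the ED followed by discharge without admission". In this protocol, then, being admitted and attending ED are different things.

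Section 9.4 lists time to first ED visit under a conditional heading, "In those that had at least one ED visit", and lists time to first readmission in the same way. Section 11.6 includes everyone discharged with a device in all endpoints other than the screening one.

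**The concern.** The rule suits readmission, because a participant who is never admitted has not had that event. It does not suit the ED outcome, where the event is by definition an attendance that did not lead to admission. Many participants with a first ED visit will therefore meet the stated condition for censoring. Others, admitted without ever having a counted ED visit, meet neither the event definition nor the censoring condition.

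At stake is one curve and its quantiles. Objective 5 in section 8.2 is to estimate readmission, ED and GP visit rates for the planned randomised trial, so the ED curve is planning information. If the rule were programmed as written, ED-free survival would be overstated, and its quantiles would come out late or not be reached.

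**Working it through.** **1. Sample size.** Section 11.2 gives "the requirement for a minimum of 80 patients in total" and expects 20% drop-out. 80 / (1 − 0.20) = 100, which matches the planned total. The point does not depend on this figure; N = 100 is used below only to show size.

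**2. The rule applied to time to first ED visit.** Each participant falls into one of four groups.

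| Counted ED visit? | Ever admitted? | Status under the literal rule | Status the outcome needs |
|---|---|---|---|
| Yes | No | Censored | Event |
| Yes | Yes, on a separate occasion | Event | Event |
| No | Yes | None given | No ED event; handling to be stated |
| No | No | Censored | Censored |

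The rule goes wrong in the first row and is silent in the third. This follows from the text and needs no rates.

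**3. Share of ED events lost.** Let p_ED be the proportion with a counted ED visit and p_R the proportion readmitted. Assume that the two are independent.

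- Participants with an ED event: N × p_ED
- Kept by the literal rule: N × p_ED × p_R
- Wrongly censored: N × p_ED × (1 − p_R), a share of 1 − p_R
- Admitted with no counted ED visit, hence no status: N × p_R × (1 − p_ED)

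Section 7.2 gives two background 30-day readmission figures: 8% (New Zealand, primary diagnosis of AECOPD) and 21% (USA, all readmissions). The share lost is 1 − 0.08 = 92% and 1 − 0.21 = 79%. It depends on neither N nor p_ED.

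**4. Effect on the estimate.** The documents give no ED-visit rate, so 5%, 10% and 20% are assumed, with N = 100 and no drop-out. Everyone without a retained event is taken as at risk to day 30. Each range runs from p_R = 8% to p_R = 21%.

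| Assumed p_ED | True events | Kept | Wrongly censored | 30-day ED incidence, literal rule | No status |
|---|---|---|---|---|---|
| 5% | 5 | 0.4 to 1.05 | 4.6 to 3.95 | 0.4% to 1.05% | 7.6 to 19.95 |
| 10% | 10 | 0.8 to 2.1 | 9.2 to 7.9 | 0.8% to 2.1% | 7.2 to 18.9 |
| 20% | 20 | 1.6 to 4.2 | 18.4 to 15.8 | 1.6% to 4.2% | 6.4 to 16.8 |

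For example, at 10% and 21%: 10 × 0.21 = 2.1 kept, 10 × 0.79 = 7.9 censored, and 100 × 0.21 × 0.90 = 18.9 with no status. If only participants without a counted ED visit are censored, all 5, 10 or 20 events are kept and the incidence is 5%, 10% or 20%.

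**5. Sections 9.4 and 11.1.** Under the conditional headings in 9.4, everyone analysed has had the event, so nobody could be censored for lack of it. Section 11.1 plans Kaplan-Meier with censoring, and 11.6 includes all participants discharged with a device. Both descriptions cannot hold.

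**The case against.** The strongest reply is that the intent is plain. The sentence names first ED visit as a Kaplan-Meier outcome, and a competent analyst would treat participants with the event as events and those without it as censored. On this view the reference to admission is loose shorthand carried over from the readmission outcome. That is probably what was meant, and it limits the seriousness. It does not remove the defect. The stated rule gives a wrong status for 9.4.21b, nothing elsewhere corrects it, and the intended meaning would still leave the censoring time and the handling of death or ward admission unstated. Section 12.2 expects deaths and admissions, and 11.2 expects 20% drop-out.

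The reply is also right that the percentages rest on assumed independence. If participants who attend ED are also more likely to be admitted, the loss is smaller.

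Four stronger readings are not supported:

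- A reader might infer that every ED event is lost. Participants with both a counted ED visit and a separate admission remain events.
- A reader might infer that all ED results are compromised. The endpoint "Proportion of participants with at least one ED visit within 30 days of discharge" is reported as a count and proportion, and the number of ED visits is analysed by Poisson regression. Neither uses the censoring rule.
- A reader might infer that the ED-visit definition is itself an error because it leaves out attenders who were then admitted. It is an explicit choice that avoids counting one episode twice, and those patients are captured under the readmission outcomes.
- A reader might infer that differing admission practice distorts a comparison of the two sites. The documents describe no such practice and plan no site comparison.

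**Conclusion.** The censoring rule is wrong as written for time to first ED visit. Its literal use would overstate ED-free survival and understate ED incidence. The contradiction rests on the text of 9.4 and 11.1 alone. The 92% to 79% loss is illustrative: it needs independence and takes background readmission rates as the study's own. The consequence is contained, because one secondary, descriptive outcome is affected, in an uncontrolled feasibility study with no pass/fail criteria. It is worth correcting because the correction is nearly free and removes choices that would otherwise be made at the programming stage.

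**What to change.** Split the sentence in 11.1 into two rules.

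- **Readmission (9.4.18b):** the event is the first readmission. Participants with none are censored at day 30, or at last follow-up if earlier.
- **ED visit (9.4.21b):** the event is the first ED visit as defined in 9.4. Participants with no such visit are censored at day 30, or at last follow-up if earlier. State how death or a ward admission before a first ED visit is handled, for example by censoring at that time or as a competing event.

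In 9.4, move both times out from under the conditional headings, so that they match a Kaplan-Meier analysis of all participants in the 11.6 population.

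The cost is a few sentences in 11.1 and a small rearrangement of the 9.4 list. No new data, visit or endpoint is needed, and the ED-visit definition can stay as it is.
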